3.5 Telephone Call

At 3 weeks following randomization, the site will contact the parents to determine whether the study-prescribed spectacles have been received and that the child is wearing them. The site will record the date that the new spectacles were received or document that they have not been received as of the call date. If spectacles have not been received, the site will record comments about factors involved in the delay. Sites will encourage full-time wear of the study spectacles.

3.6 Masked Examiner Testing

At the 8-week outcome visit, a Masked Examiner, who is a pediatric ophthalmologist, pediatric optometrist, or certified orthoptist, will assess the control of the exodeviation and perform PACT testing (see section 2.6.1).

The Masked Examiner must be someone *other than* the investigator.

The Masked Examiner must not verify the spectacles using lensometry, discuss compliance of spectacle wear with the participant or parents, administer the symptom or spectacle survey, access the medical history, or enter data on the study website.

Given that the study spectacles will not be concealed in any way, instructions for the masked examiner will include the importance of maintaining masking if possible; examiners should try not to inspect the participants' spectacles during testing. After completion of the masked exam testing, the masked examiner will indicate whether or not the participant appears to be wearing prism correction.

3.7 Outcome Visit Testing Procedures

All outcome assessments should be completed with the participant wearing study spectacles (i.e., prism spectacles or non-prism spectacles).

Participants will be tested in trial frames in the following cases:

- Participant did not bring study spectacles to the outcome exam
- Participant's study spectacles are outside refractive error and/or prism tolerances
- Participant lost study spectacles
- Partcipant never received study spectacles

900 Someone other than the Masked Examiner will ensure that the participant is wearing the study-901 prescribed spectacles (including plano spectacles if prescribed) before the masked exam. 902 The following procedures should be performed by the appropriate examiner (see below) and in 903 the order specified: 904 905 The following procedures are tested first by someone *other than* the Masked Examiner: 906 1. Spectacle Prescription Verification (Lensometry): Prior to performing the outcome 907

- examination, the participant's spectacle correction will be verified using a lensometer (including plano lenses). (See IXT6 Testing Procedures Manual)
 - Lenses will be measured through the viewing position by marking the pupil position on the lenses and performing lensometry at this position
 - If spectacles do not meet the tolerances listed below, the participant should be tested with trial frames with the intended prescription in place.

Prism Group

908

909

910

911

912

914

915

916

917

918 919

920

921 922

923

924 925

926

927

928

929

930

931

932

933

934 935 936

937

938

939

940 941

942

943

944

945

- Spectacle sphere, cylinder, and axis should meet the following tolerances:
 - o Sphere within 0.50D of prescribed
 - Astigmatism within 0.50D of prescribed
 - o Axis within 10 degrees of prescribed astigmatism if ≤1.00D and within 5 degrees of prescribed astigmatism if >1.00D
- Spectacle prism should meet the following tolerances:
 - \circ The **net** horizontal prism is $\leq 3\Delta$ from the prescribed prism based on Table 1 (section 3.1)
 - The **net** vertical prism is $<2\Delta$

Examples of Prism Spectacle Manufacture Tolerance

- Examples within tolerance:
 - \circ 1 Δ base-down both lenses (in addition to correct horizontal amount prescribed)
 - o 3Δ base-in right lens, 5Δ base-in left lens when 4Δ base-in for both lenses was prescribed
- Examples NOT within tolerance:
 - o 1Δ base-down right lens, 1Δ base-up left lens (in addition to correct horizontal amount prescribed)
 - ο 6 Δ base-in right lens, 5 Δ base-in left lens when 4 Δ base-in for both lenses was prescribed

Non-Prism Group

- Spectacle sphere, cylinder, and axis should meet the following tolerances:
 - o Sphere within 0.50D of prescribed
 - Astigmatism within 0.50D of prescribed
 - Axis within 10 degrees of prescribed astigmatism if \leq 1.00D and within 5 degrees of prescribed astigmatism if >1.00D
- Because unintended prism can occur due to decentration, spectacle prism should meet the following tolerances:
 - The **net** horizontal prism is $\leq 1\Delta$
 - The **net** vertical prism is $\leq 1\Delta$

2. Compliance Assessment: Compliance with spectacle wear since receiving the spectacles 956 957 will be assessed based on review of the compliance calendars and discussion with the 958 parents and child using the following scale: 959 • Excellent (76% to 100%) • Good (51% to 75%) 960 961 • Fair (26% to 50%) 962 • Poor ($\leq 25\%$) 963 3. Symptom and Spectacle Surveys: 964 A brief survey of IXT symptoms will be administered to the child. 965 A brief survey of symptoms that may be associated with prism spectacle wear 966 will be administered to the parents of the participant. Parents are asked to 967 respond to the survey questions based on their observations of their child in the 968 past 2 weeks. 969 970 Once the assessments listed above are completed, the following procedures must be 971 performed in the specified order. Procedures indicated as "masked" must be tested by the Masked Examiner. Procedures not indicated as "masked" may be tested by the 972 973 Masked Examiner or another study-qualified examiner although it is preferred that they 974 be completed by the Masked Examiner. All procedures should be performed with the participant wearing the study spectacles (or trial frames if required) and without 975 976 cycloplegia: Although testing must be performed in the specified order; there is **no specified** "waiting" time 977 that needs to occur between different tests. 978 979 4. Control of the Exodeviation #1 (Masked): A Masked Examiner will assess control of 980 exodeviation at distance and near fixation using the Intermittent Exotropia Control Scale.²⁹ 981 5. Stereoacuity Testing (Masked): Stereoacuity will be assessed using the Randot Preschool stereotest at 40 cm. 982 983 6. Control of the Exodeviation #2 (Masked, see item #4) 984 The same masked examiner who assessed IXT Control #1 does this second measure of 985 control. 986 7. Cover Test (Masked): 987 Testing must be performed by a pediatric ophthalmologist, pediatric optometrist, or 988 certified orthoptist. 989 • Cover Test will be assessed in primary position at distance (6 meters) and near (1/3 m) 990 using procedures outlined in the IXT6 Testing Procedures Manual. 991 8. PACT Testing (Masked): A Masked Examiner will assess the PACT in primary position IXT6 Pilot Study Protocol v1.0 29May2019 IXT6 Pilot Study Protocol v1.0

3-4

Examples of Non-Prism Spectacle Manufacture Tolerance

o 1Δ base in right lens, 1 base out left lens

 \circ 2 Δ base-in right lens, 2 Δ base-in left lens

 \circ 1 Δ base up right lens, 1 Δ base down left lens

o No prism right lens, 1Δ base in left lens

• Examples within tolerance:

 \circ 2 Δ base down both lenses

• Examples NOT within tolerance:

948

949 950

951

952

953

954

955

29May2019

992 at distance (6 meters) and near (1/3 m) as outlined in the IXT6 Testing Procedures Manual.

9. Control of the Exodeviation #3 (Masked, see item #4)

• The same masked examiner who assessed IXT Control #1 & 2 does this third measure of control.

10. Fusional Convergence Amplitude Testing

- Testing must be performed by a pediatric ophthalmologist, pediatric optometrist, or certified orthoptist.
- Convergence amplitudes will be measured at distance
- Using the PEDIG-approved IXT6 prism bar, record the blur, break, and recovery points according to the IXT6 Testing Procedures Manual.

11. Suppression:

993

994

995

996

997 998

999

1000 1001

1002

1003

1004

1005

1006 1007

1008

1009

1010 1011

1014 1015

1020

1021

1022

1023 1024

1031

- Testing must be performed by a pediatric ophthalmologist, pediatric optometrist, or certified orthoptist.
- Assessment of suppression at distance using the Suppression Scale and procedures outlined in the IXT6 Testing Procedures Manual.

12. Distance Visual Acuity Testing:

• Monocular distance visual acuity testing without cycloplegia will be measured using the same method used at enrollment.

3.8 **Additional Visits**

1012 Investigators may schedule additional visits at their discretion, although no data will be entered 1013 on the website

3.9 **Surgical or Non-Surgical Treatment**

Strabismus surgery and non-surgical treatments for IXT, other than the study-prescribed 1016 1017 spectacles, are not allowed during the study. If the investigator feels that additional treatment 1018 is needed outside of study guidelines, please contact a study chair for further clarification. 1019

Treatment of Amblyopia

Given the exclusion of participants with amblyopia and the short duration of the trial, no treatment for amblyopia is allowed during the study.

Management of Refractive Error

1025 Because of the short duration of the study, the spectacles prescribed at randomization may not be changed or discontinued without contacting a protocol chair. 1026 1027

1028 In the event that spectacles are lost or damaged after randomization but before the outcome 1029 visit, the spectacles may only be replaced with the same spectacle prescription that was 1030 prescribed at randomization.

1032 **CHAPTER 4 MISCELLANEOUS CONSIDERATIONS IN FOLLOW-UP**

1033 1034

4.1 **Contacts by the Jaeb Center for Health Research and Sites**

1035 The Jaeb Center serves as the PEDIG Coordinating Center. The Jaeb Center will be provided 1036 with the parent's contact information. The Jaeb Center will contact the parents of the

participants only when necessary. Permission for such contacts will be included in the Informed 1037 1038

Consent Form. The principal purpose of the contacts will be to develop and maintain rapport with the participant and/or family and to help coordinate scheduling of the outcome examination.

1039 1040 1041

1042

1043

The site investigator or coordinator will directly contact the parents of each participant 3 weeks after randomization to determine if the spectacles have been received, if the child is wearing the spectacles, and whether there are any concerns. Full-time wear of the spectacles will be encouraged.

1044 1045 1046

1047

1048

1049

1050

1051

1052

4.2 **Participant Withdrawals**

Parents may withdraw their child from the study at any time. This is expected to be a very infrequent occurrence in view of the study design's similarity to routine clinical practice and the short duration of the study. If the parents indicate that they want to withdraw their child from the study, the investigator personally should attempt to speak with them to determine the reason. If their interest is in transferring the child's care to another eye care provider, every effort should be made to comply with this and at the same time try to keep the child in the study under the new provider's care.

1053 1054 1055

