Additional Eligibility Criteria for Randomization Based on Prism Adaptation Testing

- Exodeviation by PACT while wearing "trial" relieving prism for 30 minutes is smaller at distance or near than measured during initial testing (e.g. not fully adapting to prism at both distances)
- No new esotropia on cover test at near while wearing "trial" relieving prism for 30 minutes, compared with enrollment measurement taken without prism
- No esodeviation $>6\Delta$ on PACT at near while wearing "trial" relieving prism for 30 minutes

Sample size

- 410 Up to 100 participants will be enrolled for same-day prism adaptation testing until up to 64 411 participants meeting the randomization eligibility criteria based on the prism adaptation test are 412 randomized (32 per treatment group).
- 414 Treatment Groups
- Als Randomization (1:1) to the following groups:
- Prism Group: Spectacles with refractive correction AND base-in relieving prism (40% of the greater of the exodeviation by PACT at distance or near) equally divided between the 2 lenses

• Non-prism Group: Spectacles with refractive correction (or plano spectacles if no significant refractive error) and no prism

421 422

424

Visit Schedule

- Enrollment Visit
 - If eligible, Randomization (same day as enrollment visit or within 7 days)
- 3-week phone call (21 to 28 days) after randomization
 - Outcome Exam: 8 weeks (± 2 weeks) after randomization

426 427 428

429

Testing Procedures

Distance and near control of IXT (3 measurements), near stereoacuity, distance and near cover test, and distance and near PACT will be measured by a study-qualified examiner at enrollment, and by a Masked Examiner at 8 weeks. The prism adaptation test will be assessed by a study-qualified examiner at enrollment. Distance visual acuity, fusional convergence amplitude, and suppression will be assessed by a study-qualified examiner at both visits. In addition, symptoms of headache, eye strain, dizziness, nausea, and problems with spectacle wear will be assessed at both visits.

437 438

Primary Analysis

• A comparison of mean distance control scores (mean of 3 assessments over the exam) between the prism group and the non-prism group at 8 weeks.

440 441 442

443

444

445

446

439

Secondary Analyses

- A comparison of the proportion of participants showing a "treatment response," defined as an improvement of ≥1 point in distance control (mean of the 3 assessments over the exam) between enrollment and 8 weeks.

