5.5.6 Fusional Convergence

- 1225 As an exploratory analysis, the distribution of fusional convergence amplitude (break point, blur
- 1226 point, and recovery) will be described, and compared between treatment groups for the
- 1227 enrollment exam and the outcome exam for each treatment group.

1228 1229

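### At 8 weeks the Masked Examiner is preferred but not required for fusional convergence, suppression and visual acuity, leaving a minor, reducible risk of observer bias in these additional outcomes

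*Protocol*

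**What the plan says.** Protocol section 3.7 divides the 8-week tests into two classes. For the first the rule is firm: "Procedures indicated as 'masked' must be tested by the Masked Examiner". Items 4 to 9 (the three control assessments, stereoacuity, cover test and PACT) carry that tag. Untagged procedures may be done by the "Masked Examiner or another study-qualified examiner although it is preferred that they" be done by the Masked Examiner. The heading "10. Fusional Convergence Amplitude Testing" has no tag, and neither do item 11 (suppression) and item 12 (distance visual acuity).

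The synopsis (section 1.15) is consistent with this. It says that visual acuity, fusional convergence and "suppression will be assessed by a study-qualified examiner at both visits". The flow chart (section 1.16) also leaves the three tests untagged.

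The planned analyses compare arms. Protocol section 5.5.6 says that fusional convergence "will be described, and compared between treatment groups for the" two exams, and sections 5.5.5 and 5.5.8 describe suppression and visual acuity by group. SAP section 4 goes further: an ANCOVA difference with a 95% confidence interval for convergence and visual acuity, and a bootstrap interval on the arm difference for suppression.

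**The concern.** Section 3.6 keeps the Masked Examiner away from lensometry, compliance discussion, the surveys, the medical history and website entry, and requires someone other than the investigator. None of these limits applies to the other study-qualified examiner. That person could be the investigator, or whoever has just measured the prism in the child's lenses.

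Enrollment testing precedes randomization, so knowledge of the arm can act only on the 8-week reading, and adjusting for the baseline value cannot remove it. If sites use the permission, the estimated difference for these outcomes would mix any treatment effect with examiner expectation. No planned analysis separates masked from unmasked readings. The masking assessment (protocol section 5.5.12, SAP section 5.4) covers masked examiners only, so it would not show how often someone else did the testing.

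**Working it through.** The documents state no figure on this point, so there is none to reproduce. The check is mainly textual, followed by an illustration of size.

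**1. Could the Masked Examiner do these tests?** For items 10 and 11 section 3.7 requires: "Testing must be performed by a pediatric ophthalmologist, pediatric optometrist, or certified orthoptist". Section 3.6 begins: "At the 8-week outcome visit, a Masked Examiner, who is a pediatric ophthalmologist", and goes on to name the same other two professions. Item 12 names no profession. The tests must be run in the listed order, so the Masked Examiner has just finished the third control assessment when item 10 starts. Credentials and timing are therefore no obstacle.

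**2. Does lower-tier status explain the missing tag?** Not by itself. Near stereoacuity is also only an additional analysis (protocol section 5.5.4), yet it is tagged as masked.

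**3. Can the permission reach the primary outcome?** No. Distance control comes from items 4, 6 and 9, all tagged and all done before items 10 to 12. The proceed guideline in section 5.2.1 uses the difference in distance control, with side effects also considered.

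**4. Illustrative size.**
- Input from the protocol: 30 per arm expected for analysis (section 5.1).
- Assumption 1: unmasked testing of every child would shift the arm difference by b = 0.2 to 0.5 SD.
- Assumption 2: a share f of tests, equal in both arms, is unmasked. The documents do not give f, so it runs from 0 to 1.
- SE of an unadjusted standardised difference = sqrt(1/30 + 1/30) = sqrt(2/30) = 0.258 SD.
- Shift in SE units = b × f / 0.258.

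The last column is the chance that a nominal 95% interval excludes zero when there is no true effect (normal approximation).

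| Share unmasked f | Shift, b = 0.2 to 0.5 SD | Interval excludes zero |
|---|---|---|
| 0 | 0 SE | 5% |
| 0.25 | 0.19 to 0.48 SE | 5.4% to 7.7% |
| 0.5 | 0.39 to 0.97 SE | 6.7% to 16.2% |
| 1 | 0.77 to 1.94 SE | 12.1% to 49.1% |

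The table is a scale, not a forecast. ANCOVA adjustment would change the SE, and suppression is a four-level score analysed by bootstrap, so the formula is only a rough guide there. Section 2.5 lets a child enroll without completing convergence or suppression testing, so fewer than 30 per arm may contribute to those two outcomes.

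**The case against.** The strongest reply is that this is an open, coherent choice with a sensible default. The sentence that grants the permission also states a preference for the Masked Examiner, and section 3.7, the synopsis and the flow chart agree. Convergence and suppression are labelled exploratory in the protocol, SAP section 4 reports no p-values for these comparisons, and none of the three outcomes appears in the study objective. All of that stands, and it sets the priority.

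Two further replies also stand in part. First, masking is imperfect for everyone. Section 3.6 opens its instruction on masking with "Given that the study spectacles will not be concealed in any way", so the Masked Examiner may infer the arm too, and the change would reduce the risk without removing it. Second, the procedures for convergence and suppression are in a testing manual that is not among the documents. SAP section 4 (fusional convergence) defines the amplitude by the prism that induces blur or diplopia, which involves the child's own perception. How far each reading depends on the examiner cannot be settled here, nor whether the case report form already records who tested.

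A reader might infer that these comparisons are in fact biased and that the bias is wholly avoidable. The documents do not support that: they show a permission, not how often it is used. A reader might also take convergence and suppression to be the decisive evidence on mechanism. Section 1.4 calls the mechanism largely unknown and mentions weaker suppression only as a possibility.

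The replies do not explain why an equally qualified Masked Examiner, already testing the child, should be optional for outcomes on which arm differences will be reported.

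**Conclusion.** The point holds as a minor risk of observer bias in three additional outcomes that can be reduced at little cost. The primary outcome and the proceed guideline are unaffected. Under the assumed 0.2 to 0.5 SD shift and 30 per arm, the effect on an unadjusted standardised difference lies between 0 SE and 0.8 to 1.9 SE, and the upper range applies only if every test is unmasked. Both the shift and the unmasked share are assumptions with no anchor in the documents. Priority: low.

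**What to change.** Tag items 10 to 12 as masked in section 3.7 and in the flow chart (section 1.16), and align the testing paragraph of the synopsis (section 1.15). For any exception, record on the form who did the test and whether that person was masked. In the report, state that masking was partial because the spectacles were visible. For visits already held, give the tester's masking status where it can be established, and otherwise name the limitation beside these estimates.

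The cost is protocol wording, one form field if none exists, and a few more minutes of the Masked Examiner's time per visit. No test is added and the required order does not change. The documents do not say how available Masked Examiners are, which is why a recorded exception is better than an absolute rule.

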4.3 Risks

There are no risks that would exceed standard of care treatment involved in this study when treating with either prism or non-prism spectacles.

1057 1058 1059

1060

1056

4.3.1 Risks of Examination Procedures

The procedures in this study are part of daily eye care practice in the United States and pose no known risks.

1061 1062 1063

1064

4.3.2 Risk of Prism Therapy

The risks involved in the study are identical to those for a child treated with prism therapy who is not participating in the study.

1065 1066 1067

Some participants treated with prism may experience eye strain or notice distortion when wearing the spectacles: these typically dissipate over time and also with removal of the spectacles.

1069 1070 1071

1068

4.3.3 Risk Assessment

1072 It is the investigators' opinion that the protocol's level of risk falls under DHHS 46.404, which is 1073 research not involving greater than minimal risk.

1074 1075

4.4 **Reporting Adverse Events**

1076 Although no adverse events are anticipated as a result of prism therapy or non-prism spectacle 1077 wear, any new cases of amblyopia or new cases of constant esotropia will be reported. No

surgical procedures are part of the protocol and no treatments are being prescribed that are not part of usual care. Investigators will abide by local IRB reporting requirements.

4.5 Discontinuation of Study

The study may be discontinued by the Steering Committee (with approval of the Data and Safety Monitoring Committee) prior to the pre-planned completion of enrollment and follow-up of all participants.

4.6 Travel Reimbursement

The parent of each participant enrolled in the study (i.e., undergoing prism adaptation testing) will be compensated \$50 (by gift card or check) for completing the Enrollment Exam, regardless of whether the participant is randomized. The parent of each randomized participant will also receive an additional \$50 (by gift card or check) for completing the 8-week outcome visit. If there are extenuating circumstances, and the participant is unable to complete the 8-week outcome visit without additional funds due to travel costs, additional funds may be provided.

